 - Sensitivity of Avantect test for detecting PC – number of individuals in the intervention arm with one or more Avantect “detected” test results and PC divided by the number of individuals in the intervention arm with PC.
 - Specificity of Avantect test for ruling out PC – number of individuals in the intervention arm with no Avantect “detected” test results, at least one Avantect “not detected” test result and no diagnosis of PC divided by the number of individuals in the intervention arm with no diagnosis of PC.
 - Resectability rate – number of individuals with PC deemed resectable by the study multidisciplinary team (MDT) divided by the number of PCs.

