2.3 SECONDARY STUDY OBJECTIVES AND ENDPOINTS

To evaluate the Avantect test in detecting pancreatic cancer in the entire study cohort (Pilot + Study Stage 1 + Study stage 2 combined) in terms of:

- Stage shift (the proportion of pancreatic cancers diagnosed at stage I/II out of all pancreatic cancers) - compared between arms
- PPV – intervention arm only
- NPV – intervention arm only
- Proportion of pancreatic cancer patient undergoing surgical resection – compared between arms

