Two of the three co-primaries are metrics of test accuracy. In practice test results will not be available for all participants due to machine failure, insufficient blood sample quality, shipping or processing, or participants being unable to provide a blood sample. To reduce the number of participants where no test results are available, three collection time points are included. In the case where a blood draw did not occur or the sample was not analysable following a scheduled visit, a repeat blood draw will be arranged. The expected proportion of participants who are expected to not have a single Avantect result is 2.5%.

Using the PropTestPower function in the R package EnvStats, it was determined that 73 individuals with pancreatic cancer are required in each arm to detect a change of resectability from 14% in usual care to 40% in the intervention arm. At the stage 2 final analysis, allowing for interim analysis, the overall power would be 96.5%. Allowing for 2.5% loss to arrive at the Per Protocol population (see section 9.4), this increases to 75 cases per arm (150 total), which at an event rate of 1% leads to a recruitment target of 7,500 per arm (15,000 total). As only samples from the intervention arm are to

be tested for the purpose of the analysis, with an anticipated test sensitivity of 65% and specificity of 95%, this leads to the following confusion matrix in the intervention per protocol group (7,312):

		Diagnostic status	
		Has PC diagnosis	Does not have PC diagnosis
Avantect test result	Detected	48	362
	Not detected	25	6,877

With 73 cases of pancreatic cancer of which $48/73 = 65\%$ were detected by the Avantect test, this would be sufficient to rule out a sensitivity lower than 42 % in the stage 2 final analysis at 96.5% power. On discussion with the FDA, a specificity of 92% would be considered acceptable within this clinical context. With 6,877 individuals without a pancreatic cancer diagnosis of which $6,877/7,239 = 95\%$ are expected to be detected by the Avantect test, more than 99% power is achieved to rule out a specificity lower than 92%.

Definition of ‘promising result’ in study stage 1 to guide progression to study stage 2

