9.4 STATISTICAL ANALYSIS PLAN (SAP)

This study will be analysed using the principles of the International Conference on Harmonisation E9 guidelines and reported according to the CONSORT guidelines. A full and detailed statistical analysis plan will be developed prior to the final analysis of the study. The main features of which are described here.

All analyses will be conducted on a Per Protocol population. All individuals in the control arm will qualify for the Per Protocol population. Individuals in the intervention arm will qualify for the Per Protocol population if they have at least one analysable Avantect test result (i.e. either “Detected” or “Not detected”). Per Protocol population will be analysed according to the original randomisation

group even when other aspects of the protocol are not followed e.g.unplanned cross-over, study withdrawal. It is expected that 98.8% of the randomised population will qualify for the Per Protocol population.

The co-primary outcomes are Avantect sensitivity and specificity in detecting PC, and resectability rate. Sensitivity is defined as the proportion of participants in the intervention arm with one (or more) Avantect “detected” test results who have pancreatic cancer diagnosed via imaging in relation to all individuals in the intervention arm who had pancreatic cancer diagnosed. Specificity is defined as the proportion of participants in the intervention arm with one or more Avantect “not detected” test results, and no Avantect “detected” results, who did not have a pancreatic cancer diagnosis in relation to all individuals in the intervention arm who did not have a pancreatic cancer diagnosis. Resectability is defined as the proportion of PCs deemed resectable by the study MDT divided by the number of PCs and will be compared between arms. For all co-primary endpoints, a logistic model will be used to estimate uncertainty. At the stage 1 interim analysis, due to alpha spending to reach a cumulative total alpha of 0.025 for each co-primary endpoint, a one-sided 98.6% confidence interval will be calculated to estimate the lower-bound of the observed proportion. At the stage 2 final analysis, a one-sided 98.5 % one-sided interval will be calculated instead. Co-primary endpoints will also be assessed for regular oversight meetings, where a one-sided 95% confidence interval will be used.

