At the stage 1 interim analysis, co-primaries will be considered ‘futile’, ‘promising’ or ‘efficacious’ according to the following table:

	Expected proportion	Futility threshold at stage 1	Promising result range at stage 1	Efficacy threshold at stage 1
Sensitivity	65%	<46.5%	46.5% to 63.1%	>63.1%
Specificity	95%	<92.0%	92.0% to 94.9%	>94.9%
Resectability	40%	<21.0%	21.0% to 38.1%	>38.1%

At the stage 2 final analysis, the sensitivity co-primary will be considered successful if a sensitivity of 49% can be ruled out with a one-sided p-value of 0.03 among participants in the intervention arm. Specificity will be considered successful if a specificity of 92% can be ruled out with a one-sided p-value of 0.03 among participants in the intervention arm. Resectability will be considered successful if the resectability rate in the intervention arm is higher than the rate in the control arm at a one-sided p-value of 0.03.

Secondary outcomes, in order of importance, are defined as follows, which all are calculated with a minimum of 90% power:

Stage shift - The analysis will be conducted by comparing the proportion of PC cases diagnosed at stage I/II vs III/IV between the intervention and control arms. A proportion of 60% (44/73 PCs) is expected in the intervention arm versus 35% (26/73 PCs) in the control arm, which provides 90% power at a one-sided alpha of 0.05. Stage shift will be considered successful if the proportion in the intervention arm is higher than the rate in the control arm at a one-sided p-value of 0.05.

PPV in detecting PC - The analysis will be conducted within the intervention arm. With a sample size of 7,500, PC prevalence of 1%, and 2.5% lost from the per protocol population, there will be an expected 410 individuals with an Avantect “detected - abnormal” result. 11.6% (48/410) are expected to have a PC. PPV will be considered successful if a null PPV of 5% can be ruled out at a one-sided p-value of 0.05.

NPV in ruling out PC - The analysis will be conducted within the intervention arm with a sample size of 7,500, PC prevalence of 1%, and 2.5% lost from the per protocol population, will be an expected 6,902 individuals without an Avantect “detected - abnormal” result. 99.6% (6,877/6,902) are expected to not have a diagnosis of PC. NPV will be considered successful if a null NPV of 99% can be ruled out at a one-sided p-value of 0.05.

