Resection rate of PC. The analysis will be conducted by comparing resection between the intervention and control arms. With a sample size of 15,000, PC prevalence of 1%, and 2.5% lost to follow-up, there will be an expected 73 cases of PC in each arm. It is assumed that 5% of those deemed resectable will not undergo resection, for an expected rate of 38% (28/73) in the Intervention arm versus 13% (9/73) in the control arm. Resection rate will be considered successful if the proportion in the intervention arm is higher than the rate in the control arm at a one-sided p-value of 0.05.

For analyses of exploratory outcomes, the following applies:

Time-to-event outcomes (time to PC diagnosis and overall survival) will be analysed using a Cox regression model to determine the hazard ratio (and 95% confidence interval) between groups. This will be supported by a Kaplan-Meier plot for each group, median survival (and 95% confidence intervals), and estimates of 3-year survival (T0-T3) (alongside the difference in proportions and corresponding 95% confidence interval). The 6-item STAI will be analysed using a t-test or non-parametric suitable alternative if data are not normally distributed. Performance characteristics for high-grade neoplasia include sensitivity, specificity, PPV and NPV. They will be analysed as described

SAFE-D Clinical Performance Study Protocol Version 4, IRAS Ref: 326332 31-JUL-2025 Page 49 of 68

above, when high-grade neoplasia is also considered as Disease Positive, and when high-grade neoplasia alone (with the exclusion of pancreatic cancer) is considered as Disease Positive. Two-sided p-values will be presented for exploratory outcomes.

Unless otherwise stated, continuous data will be presented as means and standard deviations and analysed using a linear regression modelling framework. If data are skewed, medians and ranges will be presented. To analyse skewed data we will attempt to find a suitable transformation to allow a linear modelling approach. If this is not possible, we will explore whether another suitable parametric distribution fits the data. If not, a non-parametric approach, such as quantile regression, will be used. Binary data will be reported in terms of odds ratios and analysed using logistic regression modelling, unless otherwise stated.

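### Resectability, stage shift and resection are compared only as shares of diagnosed cancers; add a supportive comparison of late-stage cancer per randomised participant

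*Protocol*

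**What the plan says.** Protocol section 2.2 defines resectability as the "number of individuals with PC deemed resectable by the study multidisciplinary team (MDT) divided by the number of PCs". Section 2.3 defines stage shift as "the proportion of pancreatic cancers diagnosed at stage I/II out of all pancreatic cancers", and the resection endpoint (sections 2.4 and 9.4) has the same denominator. All three are compared between arms.

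Section 9.2 states that "73 individuals with pancreatic cancer are required in each arm to detect a change of resectability from 14% in usual care to 40" per cent, and that at the final analysis "the overall power would be 96.5" per cent. The resection paragraph of section 9.4 repeats the equal counts: "there will be an expected 73 cases of PC in each arm".

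Resectability succeeds in section 9.4 if "the resectability rate in the intervention arm is higher than the rate in the control arm at a one-sided p-value of 0.03". For the same analysis that section also says "a one-sided 98.5 % one-sided interval will be calculated instead", which corresponds to 0.015. Uncertainty for the co-primaries is to come from a logistic model. Stage shift is expected at 44/73 against 26/73 and is judged at one-sided 0.05.

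Three other places bear on the point:
- **Testing and imaging.** Only intervention-arm samples are tested, and only participants with a detected result are referred for pancreatic imaging. Control samples are stored (synopsis, sections 7.8.1 and 9.3).
- **Case definition.** Section 7.9.3 counts IPMN or MCN with high-grade dysplasia at surgery as pancreatic cancer (PC). The exploratory endpoint in section 2.4 treats high-grade mucinous cysts as separate from PC.
- **Time to PC diagnosis.** Section 2.4 labels it as within the intervention arm. Section 9.4 plans a hazard ratio between groups, with three-year estimates and a difference in proportions.

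**The concern.** The trial randomises participants, but these endpoints divide by a count that arises after randomisation and that testing can change. Assuming 73 PCs in each arm amounts to assuming that the whole gain in resectability comes from fewer unresectable cancers. If testing and imaging also bring in cases that the control arm does not show by 36 months, each adds to numerator and denominator and no advanced cancer is prevented.

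The protocol itself contains one possible source. Section 1.2 says the test may detect some neoplastic cysts, and section 7.9.3 counts operated high-grade ones as PC. Cancers that would surface only after 36 months would act in the same way.

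At stake is how a success would be read. No endpoint compares late-stage or unresectable cancers per randomised participant, and that number should fall if detection is truly earlier.

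**Working it through.** **1. The plan's own figure.** Inputs (sections 9.2 and 9.4): 73 PCs per arm, 14% against 40%, one-sided 0.03 (z = 1.881), pooled rate 27%.

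Power = Φ{[0.26 − 1.881·√(2·0.27·0.73/73)] / √[(0.14·0.86 + 0.40·0.60)/73]} = Φ{(0.26 − 0.138)/0.0703} = 95.9%, close to the stated 96.5%.

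**2. What equal counts imply.** Unresectable cancers: 73 × 0.86 ≈ 63 (control) and 73 × 0.60 ≈ 44 (intervention), a ratio of 0.70. Stage III/IV cancers: 73 − 26 = 47 and 73 − 44 = 29.

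**3. Resectability with no fewer unresectable cancers.** Control is 10/73, with 63 unresectable. Keep 63 in the intervention arm and add e resectable cancers there only. The number e is an assumption.

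Logistic Wald: z = ln[(10 + e)/10] / √[1/(10 + e) + 1/63 + 1/10 + 1/63].

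| e | Intervention | Control | One-sided p |
|---|---|---|---|
| 10 | 20/83 = 24.1% | 13.7% | 0.052 |
| 12 | 22/85 = 25.9% | 13.7% | 0.0305 |
| 13 | 23/86 = 26.7% | 13.7% | 0.0233 |
| 15 | 25/88 = 28.4% | 13.7% | 0.0135 |
| 32 | 42/105 = 40.0% | 13.7% | 0.0001 |

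The smallest e that meets 0.03 is 13 by Wald, 12 by pooled z (p = 0.0287) and 14 by Fisher (p = 0.0248), or 16% to 19% more than 73. At 0.015 it is 15 (Wald and pooled z) or 16 (Fisher). With 32 extra, the planned 40% is reached while 63 unresectable cancers remain in each arm.

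**4. Stage shift with no fewer late-stage cancers.** Control is 26/73, with 47 late in each arm. With 19 extra early cancers the rates are 45/92 = 48.9% and 35.6%; z = ln(45/26)/√(1/45 + 1/26 + 2/47) = 0.549/0.321 = 1.71, p = 0.044. Fisher needs 21. That is 26% to 29% more than 73.

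**5. Range over the assumption.** If the excess averaged 10, 20 or 30 early, resectable cancers with no change in advanced disease, the chance of meeting the resectability rule at 0.03 would be about 40%, 83% and 97%. For stage shift at 0.05 it would be about 25%, 56% and 80% (normal approximation).

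**6. Power per randomised participant under the planned effects.** The denominator is the plan's 7,312 per arm.
- Unresectable PC, 62.8 against 43.8: the difference is 0.00260, standard error 0.00141; Φ(0.00260/0.00141 − 1.881) ≈ 49% at one-sided 0.03.
- Stage III/IV PC, 47 against 29: the difference is 0.00246, standard error 0.00119; Φ(0.00246/0.00119 − 1.645) ≈ 66% at one-sided 0.05.

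**The case against.** The strongest case against has four parts.

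- **The size of the excess is assumed.** This stands: no section gives one. Section 4 says most pancreatic cancers in this population are diagnosed within 12 to 18 months of the diabetes diagnosis, and the final analysis waits for three years, two years past the last blood draw. Much pure lead time would be made up by then. Thirteen extra cases would be over a quarter of the 48 test-detected cancers expected in section 9.2 (13/48 = 27%). If only some 60% of the extra cases were resectable, about 26 would be needed: 16 resectable and 10 not give 26/99 against 10/73, Wald p = 0.024. Later-surfacing, indolent or high-grade cystic lesions are not removed by longer follow-up.
- **A between-group time-to-PC analysis is already planned.** This stands in part. A reader might infer that the trial has no means of telling a true shift from added detection. The documents do not support that: the section 9.4 analysis could show an excess of cancers, and the counts behind each proportion allow unresectable cancers to be worked out by subtraction. But section 2.4 confines the outcome to the intervention arm, and neither section counts late-stage cancers.
- **All three co-primaries must succeed.** This gives no protection. If 13 extra cancers are all test-detected, sensitivity rises from 48/73 = 65.8% to 61/86 = 70.9%.
- **Supportive tables can be left to the SAP.** True in general. Here the endpoint definitions and success rules are fixed in the protocol, and the rules as written can be met with no fewer advanced cancers.

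**Conclusion.** The point holds as a cheap improvement. The three between-arm cancer endpoints depend on a denominator that the intervention can enlarge, and a modest excess would suffice: 12 to 14 extra resectable cancers for resectability at 0.03 (15 or 16 at 0.015), and 19 to 21 extra early cancers for stage shift. These figures assume the plan's control-arm counts, no change in advanced cancers, and that every extra case is resectable or early.

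A reader might go further and infer that such an excess will occur, or that a positive result would be spurious. The documents do not support either. They give no excess, and a true fall from 63 to 44 unresectable cancers would also meet the rule. What they show is that the stated criteria alone do not distinguish the two.

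**What to change.** Keep the resectability co-primary and its test. In sections 2.3 and 9.4:

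1. Add a pre-specified supportive comparison by arm, in all randomised participants, of the 36-month cumulative incidence of stage III/IV PC and of all PC. Give each as a difference or ratio with a confidence interval. The registry fields in section 7.6.4 include diagnosis date and stage.
2. Add unresectable PC where review by the multidisciplinary study team gives resectability status in both arms. The registry fields do not include resectability.
3. Reconcile sections 2.4 and 9.4 so that PC incidence is compared between arms. Reconcile section 7.9.3 with section 2.4 on whether operated high-grade cysts count as PC.
4. State that a resectability or stage-shift success will be interpreted alongside these estimates and intervals, without a significance gate.

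The cost is wording and one table. The downside is lower power than the proportions have: about 49% for unresectable and 66% for stage III/IV PC under the planned effects. The comparison should therefore be supportive and not a fourth co-primary.

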2.3 SECONDARY STUDY OBJECTIVES AND ENDPOINTS

To evaluate the Avantect test in detecting pancreatic cancer in the entire study cohort (Pilot + Study Stage 1 + Study stage 2 combined) in terms of:

- Stage shift (the proportion of pancreatic cancers diagnosed at stage I/II out of all pancreatic cancers) - compared between arms
- PPV – intervention arm only
- NPV – intervention arm only
- Proportion of pancreatic cancer patient undergoing surgical resection – compared between arms

2.4 TABLE OF ENDPOINTS/OUTCOMES PILOT

	Objective	Outcome Measures	Summary method(s)
Primary	To determine the recruitment rate	Recruitment rate	
 Percentage recruited of all participants invited Number of individuals recruited per month

STUDY STAGE 1 and 2 (analysis inclusive of pilot):

	Objective	Outcome Measures	Summary method(s)
Primary	To estimate the proportion of PCs deemed resectable	Resectability rate	Percentage of PCs deemed resectable by the study MDT [compared between arms]
	To estimate the sensitivity of the Avantect test in detecting PC	Sensitivity	Percentage with PC diagnosed who have an Avantect “detected” result [within intervention arm]
	To estimate the specificity of the Avantect test in ruling out PC	Specificity	Percentage without PC diagnosed who have one or more Avantect “not detected” results and no Avantect “detected” results [within intervention arm]
Secondary	To determine the effect of the Avantect test on PC stage shift	Stage shift	Percentage of PCs diagnosed at stage I/II [compared between arms]
	To estimate the PPV of Avantect for detecting PC	PPV	Percentage with an Avantect “detected” result who have PC diagnosed [within intervention arm]

	To estimate the NPV of Avantect for ruling out PC	NPV	Percentage of individuals with no Avantect “detected” test results who have no diagnosis of PC [within intervention arm]
	To estimate the proportion of PCs that are resected	Resection	Percentage with PC who underwent resection [compared between arms]
Exploratory	To estimate the time from NOD diagnosis to PC diagnosis	Time to diagnosis	Kaplan-Meier curve Hazard ratio [within intervention arm]
	To estimate the overall survival of study participants	Overall Survival	Kaplan-Meier curve Hazard ratio [compared between arms]
	Assess the effect of the Avantect test on state anxiety over time	6-item STAI	T-test or non-parametric alternative if suitable [compared between arms]
	To investigate the performance characteristics for high-grade neoplasia	Sensitivity Specificity PPV NPV	As described above, but disease positive is defined as PC and/or high-grade mucinous cysts and non-cases defined as no pancreatic cancer or high-grade mucinous cysts. This will be repeated where high-grade mucinous cysts are considered as disease positive and PCs are excluded. [within intervention arm]

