Clinical Performance Study Design:	Prospective, single blinded interventional randomised multicentre study
Sample size:	Up to 15,000 participants across the UK in the following stages: 
 • Pilot: target 800 participants • Study stage 1: up to an additional 5,600 participants • Study stage 2: up to an additional 8,600 participants There will be a data driven ‘stop-go’ decision at the end of each stage before progressing to the next stage.
Treatment/Intervention:	Participants will be blindly randomised into two arms; 
 • Intervention arm: Avantect test performed within prioritised time frame with intent to share only “detected” test results with the participants and their General Practitioners (GPs) in parallel to making a referral to the local secondary care clinical team for further investigations. All test results will be included in primary endpoint analysis. • Control arm (Standard of Care [SoC] arm): Participants will receive the current standard of care for diabetes management. Samples will be used for potential future Avantect testing and/or future research.
Number of specimens required per participant:	Three peripheral blood samples per participant (up to 30 mL in total) will be collected at three timepoints
Duration of the clinical performance study:	Participant involvement on trial: 3 visits over 12 months Length of remote follow-up collection for each participant: 36 months from consent Recruitment duration: 36 months Total study duration (including 12m analysis and report writing): 7 years

URL for Database:	https://www.imedidata.com
URL for randomisation:	https://www.imedidata.com

Primary Study Endpoints:	Pilot: Recruitment rate Study stage 1 & 2: Sensitivity and specificity of Avantect test for detecting pancreatic cancer, pancreatic cancer resectability rate
---------------------------------	--

Secondary Study Endpoints:	Secondary endpoints (pilot and study stage 1 and 2 combined) will include pancreatic cancer stage shift, PPV, NPV and proportion of pancreatic cancer patients undergoing surgical resection
Exploratory Endpoints	Overall survival (time-to-event) Time to pancreatic cancer diagnosis (NOD to pancreatic cancer diagnosis) 6-item Spielberger State Trait Anxiety Inventory (STAI) Performance characteristics for high-grade neoplasia
Total Number of Sites:	Up to 3,000 GP practices and up to 200 Specialist Diabetes Service Centres

TRIAL SCHEMA

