5.3 INCLUSION CRITERIA

1. 50 – 84 years of age at the time of enrolment (within year of birth, not month of birth)
2. Haemoglobin A1c (HbA1c) \geq 48 or 6.5% and/or confirmed type II DM diagnosed within the last 180 days (+20 days flexibility allowance)
3. Willing to provide up to 30 mL of blood for each study visit
4. Willing and eligible to undergo MRI scan (or CT scan if MRI is contraindicated)
5. Understands the study process and is willing to take part in the study and sign the informed consent form

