5.4 EXCLUSION CRITERIA

6. Prior type I or type II DM diagnosis > 6 months
7. A history of pancreatic cancer, pancreatic neuroendocrine tumour (pNET) or Pancreatitis
8. Under investigation for or confirmed pancreatic cancer / pancreatic cyst

9. Any known pancreatic surgery (not including ERCP), or other major surgery requiring anaesthesia within 3 months
10. Any invasive solid or haematological cancer in the past 3 years, including cancer recurrence after treatment in the last 3 years
11. Current chronic or acute oral or systemic steroid use within 3 months of initial HbA1c or diabetes diagnosis (estimate rather than accurate)
12. Blood transfusion within 1 month
13. Solid organ transplant recipient
14. Currently pregnant
15. Needing dialysis

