7. STUDY PROCEDURES

7.1 SCHEDULE OF OBSERVATIONS AND PROCEDURES

Visit:	Baseline (T0)	T1	T2	T3
Time:	Within 6 months from Diabetes mellitus (DM) diagnosis*	6 months after T0	12 months after T0	Three occasions over the study duration from consent (T0)
Eligibility evaluation	X			

Informed consent	X			
Patient Data Collection Interview ^a	X			
STAI questionnaire ^b	X	X	X	
Blood sample collection ^c	X	X	X	
Body measurements ^d	X	X	X	
Electronic Health Record Review ^e	X	X	X	
Cancer and mortality registry review				X

NB: The participant/legal representative is free to withdraw consent at any time without providing a reason. When withdrawn, the participant will continue to receive standard clinical care. Follow up data will continue to be collected (unless the participant/legal representative has specifically stated that they do not want this to happen).

*In the SAFE-D study “date of DM diagnosis” refers to the elevated HbA1c date

a: sex, ethnicity, selected pre-existing conditions of interest, family history of cancer, smoking, vaping, alcohol use

b: 6-item STAI

c: 2x10 mL Streck® tubes, 1x6 mL lithium heparin tube

d: height, weight, waist circumference

e: review of selected pre-existing conditions of interest from EHR summaries when available or participant self-reported.

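### The Kaplan-Meier curve for time to pancreatic cancer diagnosis starts at the diabetes date, but participants enter up to 200 days later without diagnosed cancer, so an ordinary curve understates early incidence

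*Protocol*

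**What the plan says.** - **Origin.** Section 2.4 gives the objective as "To estimate the time from NOD diagnosis to PC diagnosis", and the synopsis lists "Time to pancreatic cancer diagnosis (NOD to pancreatic cancer diagnosis" among the exploratory endpoints. A footnote to the schedule in section 7.1 says that the date of diabetes diagnosis "refers to the elevated HbA1c date".
- **Entry.** Section 5.3 admits people with "confirmed type II DM diagnosed within the last 180 days (+20 days flexibility allowance", so T0 may fall up to 180 + 20 = 200 days after the origin.
- **Exclusions.** Section 5.4 excludes "A history of pancreatic cancer, pancreatic neuroendocrine tumour (pNET) or Pancreatitis" and also "Under investigation for or confirmed pancreatic cancer / pancreatic cyst".
- **Method.** Section 2.4 names a Kaplan-Meier curve and a hazard ratio, within the intervention arm. Section 9.4 treats this outcome together with overall survival: a Cox hazard ratio between groups, a Kaplan-Meier plot for each group, and "estimates of 3-year survival (T0-T3"). Neither section says when a participant joins the risk set.

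**The concern.** A person diagnosed with pancreatic cancer between the HbA1c date and the T0 visit can never be enrolled. Nobody who is enrolled can have an event in that interval. If the curve starts at the HbA1c date with everyone at risk from day 0, it adds risk time in which no event could be recorded. This is left truncation. The curve then starts too low and stays low.

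The stated purpose is to describe when cancers are diagnosed after diabetes, so the curve is itself the deliverable. The error is largest in the first months, which is the period that section 4 relies on when it explains why testing is done at T0, 6 and 12 months.

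**Working it through.** **Inputs from the protocol.** Maximum lag 200 days (5.3); 1% diagnosed within 3 years and 65% sensitivity (9.2); the vast majority of diagnoses within 12-18 months of the diabetes diagnosis (4); draws at T0, 6 and 12 months (9.3). The distribution of the lag from HbA1c date to T0 is not given, so it is assumed and varied below.

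**1. The plan's own count.** 7,500 × 0.975 × 0.01 = 73.1, which reproduces the 73 expected cases per arm. The protocol states no expected figure for time to diagnosis itself.

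**2. Formula.** Let h(u) be the hazard of diagnosis at time u since the HbA1c date, and G(u) the proportion who have reached T0 by then. The true cumulative hazard is ∫h(u)du. An ordinary Kaplan-Meier curve accumulates ∫h(u)G(u)du, because only that fraction can contribute events while everyone is in the denominator.

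**3. Illustration without testing.** Assume a uniform lag over 0-200 days and 1% at 3 years, with 80% of it in the first 548 days. The early rate is 0.8%/548 = 0.00146 percentage points per day.

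- At 180 days: true 0.00146 × 180 = 0.263%; ordinary 0.00146 × 180²/(2 × 200) = 0.118%.
- After day 200 the shortfall is fixed at 0.00146 × 100 (the mean lag) = 0.146 points.

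| Time since HbA1c date | True | Ordinary curve | Relative error |
|---|---|---|---|
| 6 months | 0.263% | 0.118% | -55% |
| 12 months | 0.533% | 0.387% | -27% |
| 18 months | 0.800% | 0.654% | -18% |
| 3 years | 1.000% | 0.854% | -15% |

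The median time among 3-year cases moves from 548 × 0.5/0.8 = 342 days to 100 + 0.427/0.00146 = 392 days.

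**4. Other shapes, still without testing.** With a constant hazard and uniform lag, the shortfall beyond day 200 is 100/t: 50% at 200 days, 27% at 1 year, 18% at 18 months, 9% at 3 years. With a front-loaded hazard (85% of the 3-year hazard by 18 months) it is 55% at 200 days, 38% at 1 year and 27% at 3 years. Across early, uniform, middle and late lag distributions and windows of 180 or 200 days, the shortfall at the end of the window is 25-75% with constant hazard and 29-80% with front-loading.

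**5. The tested arm.** Keep the assumptions of step 3 and add testing: 65% sensitivity at each draw, confirmation 30 days after the draw, and cancers detectable for 180, 365 or 548 days before clinical diagnosis. The reference is diagnosis incidence from the HbA1c date under the same testing, counting also those diagnosed before they could enter. The missing pre-entry diagnoses are as many as before, but testing brings later diagnoses into the first six months, so they are a smaller share.

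| Detectable period | Ordinary curve, 6 months | Delayed-entry curve, 6 months | Delayed-entry curve, 3 years |
|---|---|---|---|
| 180 days | about -46% | about +36% | about +11% |
| 365 days | about -32% | about +64% | about +29% |
| 548 days | about -26% | about +84% | about +44% |

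The ordinary curve is about 14% low at 3 years in all three cases. Delayed entry fails here because it assumes that the hazard at a given time since the HbA1c date does not depend on when the person entered. Testing at T0 concentrates diagnoses just after entry.

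**6. Delayed entry without testing.** With constant hazard, 7,312 per arm and uniform entry, the delayed-entry curve averages 0.189% against a true 0.183% at 200 days (ordinary 0.094%), and 1.01% against 1.00% at 3 years (ordinary 0.91%).

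**7. Between-arm hazard ratio.** In the same untested setting with a true ratio of 1.5, Cox gives 1.498 with and without delayed entry.

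**The case against.** The strongest reply is that the protocol does not say late entry will be ignored. Section 9.4 gives only main features, and risk-set rules normally belong in the analysis plan. That stands as far as it goes: the protocol is silent, and an analysis plan could specify delayed entry. But the origin, the method and the eligibility rules are fixed in the protocol itself, and they do not fit together as they are. The usual repair also fails in the one arm where section 2.4 places the curve.

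It is also fair to say that the endpoint is exploratory with no success rule, that the testing schedule rests on data already published, and that the absolute error in step 3 is about 0.15 percentage points. All of this stands and limits the importance of the point.

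The T0-T3 window in section 9.4 can be read as applying to overall survival only. That reading is plausible, so this part needs clarification and is not a proven contradiction. The difference between within the intervention arm (2.4) and between groups (9.4) does not depend on it.

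**Conclusion.** The point holds for an ordinary Kaplan-Meier curve from the HbA1c date: early incidence is biased downward. The size depends on assumptions the protocol does not settle. It is about 55% at 6 months and 15% at 3 years in the untested illustration, about 25-80% at the end of the entry window across other shapes, and about 26-46% at 6 months in the tested arm.

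A reader might infer more than this, in four ways that the documents do not support:

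- That early incidence is halved as a general result. This follows only for a uniform or symmetric lag, near the end of the window, without testing.
- That the Cox comparison is also wrong. Randomisation balances the lag between arms, and no bias was found in the hazard ratio.
- That delayed entry cures the curve everywhere. In the intervention arm it overstates incidence.
- That participants enter free of cancer. They enter without diagnosed cancer; occult cancer is what the test looks for.

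No primary or secondary endpoint is affected. The change is worth making because it costs little and the curve would otherwise mislead about timing.

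**What to change.** In sections 2.4 and 9.4, make T0/randomisation the origin for the Kaplan-Meier curves and the Cox comparison of time to pancreatic cancer diagnosis, in both arms, and align the synopsis entry. State whether the hazard ratio is between arms or within the intervention arm, and which outcomes the T0-T3 estimates cover.

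If a curve from the diabetes date is still wanted, estimate it in the untested control arm with delayed entry: each person joins the risk set at T0 minus the HbA1c date. State the assumption that risk at a given time since that date does not depend on when the person enrolled. Do not use delayed entry in the intervention arm. Report time from the HbA1c date among intervention-arm cases descriptively.

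The cost is a few sentences and one extra variable for the control-arm curve. The HbA1c date underlies eligibility and T0 is a study visit, so no new visits are needed. The downsides are that the T0-origin curve no longer shows time since diabetes diagnosis directly, and that the control-arm delayed-entry curve is imprecise in the first weeks, when few people are under observation.
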